In the local randomisation approach to RDD, the fuzzy design is operationalised using the Anderson-Rubin statistic, which is the difference in the adjusted, transformed responses between units assigned to treatment and control.¹⁹ In other words, the treatment effect on the treated is identified by estimating the difference between two regression equations relating the outcome to the running variable either side of the threshold. The fuzzy approach to RDD will rely on access to good quality, patient-level onboarding data.

Basic descriptive analysis and diagnostic checks for RDD validity

Before the main analyses are carried out, diagnostic checks will be undertaken to confirm that the various assumptions of the RDD are supported.

1. **Identify the discontinuity in CO@h enrolment at age 65 and whether a sharp or fuzzy RDD is appropriate.** We will check that there is a discontinuity in the proportion of patients enrolled (ie onboarded) in CO@h at 65 years of age. We will also identify the size of this discontinuity (ie the range of discontinuity) at the threshold and whether a fuzzy design is appropriate. We will graphically show the proportion of individuals who received CO@h by weekly age. We will overlay plots of a local polynomial function either side of the threshold. These plots will be built using the 'rdplot' function from the 'rdrobust' package in R.

2. **Descriptive analysis of baseline variables, outcomes, treatment assignment and enrolment.** We will present means and standard deviations or medians, 25th and 75th quantile statistics (as appropriate). We will plot the means of the baseline variables and outcomes by week of age. We will overlay plots of a local polynomial function either side of the threshold. These plots will be built using the 'rdplot' function from the 'rdrobust' package in R, as above.
3. **Check that there is no discontinuity in the number of people by age around the threshold.** This unlikely scenario would indicate that patients could manipulate their age, potentially to gain access to the CO@h pathway. We will examine this graphically in a histogram by plotting the density of patients by weekly age in the window 1 year either side of the threshold. Following window selection (see below), we will also test whether the proportions of patients within the window are statistically comparable using a binomial test.²²

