For the procedure in (a), Cattaneo et al recommend that the p-value chosen for these tests is at least 0.10 and preferably 0.15.¹⁷ As we have a large number of baseline characteristics, a p-value of 0.10 should provide a reasonably conservative threshold, given that the chances of identifying a significant difference in at least one variable increase with the number of variables tested.²³ The results of these tests will be tabulated and plotted, showing how the minimum p-value changed against each window length from a window length of 1 week either side, up until the resulting minimum p-value remains consistently below 0.05.

Although the window selection can be done directly through the 'rdrandinf' command (within the 'rdlocrand' R package), we will calculate it using the separate window selection function 'rdwinselect', so that the window selection process is completed independently of the main analysis.²⁴

Baseline variables

The baseline variables that we will check and use to identify the age window for analysis are:

- Gender
- Ethnicity
- IMD quintile
- IMD health deprivation and disability quintile
- Smoker (yes/no)
- Obesity (yes/no)
- Diabetes (yes/no)
- Multimorbidity (yes/no), ie whether a patient had two or more long-term conditions. We will use the list of conditions in the Cambridge Multimorbidity Score,²⁵ based on a list of conditions recorded in GP records and available in GDPPR and also used in Stafford et al²⁶.
- Region – as a proxy for other unobservable characteristics, as regions may have differing rates of COVID-19 and therefore also hospital pressures, which may affect patients' outcomes.

* Using power = 80%, alpha = 5%, and two-sided test.

Main analysis

In the main analysis, we will estimate a treatment effect based on the difference in means between the treated and untreated. Using randomisation inference, 10,000 simulated draws based on Fisher's exact approach to null-hypothesis testing will be used to estimate p-values of zero effect. We do not expect to have to transform the outcomes – as we do not expect the outcomes to vary with age within the chosen window – therefore we will use a polynomial of order zero (ie a constant within-group average outcome, which is the standard in the local randomisation approach. The plots created in the prior descriptive analysis will be used to confirm this).

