The null hypothesis for the Fisher-based simulation will assume complete randomisation of patients to treatment within the window. A confidence interval will be estimated for the treatment effect by inverting the calculation for the Fisher-based p-value and identifying values of treatment effect which are not significantly different to the estimated effect. As a comparison to the Fisher-based approach, we will also estimate the p-value using the large-sample Neyman approach based on normal approximation, and also report the power of the Neyman test to inform interpretation.¹⁷ If the results of the Fisher and Neyman approaches differ, we will consider the number of observations within the window to determine which approach is most valid, with the Fisher framework being preferred where sample sizes within the window are small.

Many of our outcomes are binary. In these cases, the estimated treatment effects will comprise differences in mean outcomes on the per cent scale. For our other outcomes, the treatment effects will be differences in mean bed days. As well as the treatment effects, we will also present the point estimates for the treated and control groups in each case. We will not control for the baseline variables in the model, as the window selection procedure will already have been used to identify groups which are comparable in terms of these variables.

Calculation of intervention estimates where outcomes happen before enrolment

This evaluation aims to estimate the effect of pre-hospitalisation CO@h, as detailed in the SOP.² Although we will exclude any CCGs which are identified as only offering enrolment in CO@h at hospital discharge, it is conceivable that other CCGs may offer a combination of pre-hospital and post-discharge as part of the CO@h model, especially in those areas that had implemented a post-discharge model early on in the pandemic. There may therefore be some patients enrolled in CO@h at hospital discharge that we can identify by triangulating date of onboarding with date of hospital discharge. These patients will be considered as not having received the CO@h intervention (ie treatment receipt = 0), similar to those patients enrolled in CVWs (for whom we do not have data).

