1. Intention-to-treat analysis – we will use a sharp design (without taking account of compliance/oximeter receipt) to estimate the average effect of intervention eligibility at age 65, ie an intention-to-treat analysis.
2. Placebo outcomes – we will undertake statistical tests for treatment effects for each of the baseline variables and plot the means for each group, weekly averages and fitted constants to identify any evidence of infringement of the assumption of comparability of the groups.
3. Test of treatment assignment – we will use a binomial test to check that, within the specified window, treatment can be considered randomly assigned.
4. Influence of window choice – we will test a selection of windows smaller than the one used in the main analysis (minimum 10 patients either side of the threshold). We will not use larger windows as this may lead to biased estimates due to imbalances in baseline variables.¹⁷ By using smaller windows, this problem is avoided while also identifying whether restriction of the cohort to those increasingly closer to the threshold affects the treatment effect estimates. We will plot the resulting point estimates and confidence intervals.
5. Placebo thresholds – we will estimate treatment effects at both a lower and a higher threshold than age 65 to check that these spurious, placebo thresholds result in a treatment effect of zero. For these checks, we will only use control and treated patients,

respectively.¹⁷ We will test at thresholds centred on the first mass point past the end boundaries of the window used in the main analysis. We will use the same window size (ie number of mass points either side) as in the main analysis.¹⁷

6. Placebo study period – we will use data for a period before CO@h was implemented (ie in CCGs before they implemented CO@h) to check that there is no discontinuity in outcomes in a window around age 65 when no treatment was available. This will be a sharp RDD (as there will, by definition, be no intervention available). This sensitivity analysis will only be conducted if the intention-to-treat analysis using a sharp RDD (sensitivity analysis #1) is statistically significant.
7. Sensitivity to unmeasured confounding – we will calculate Rosenbaum’s sensitivity bounds, within the context of a local randomisation RDD, to estimate how large an unobserved confounder would need to be to affect the conclusions of the study.^{19,27}

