(White, Black, Asian, Mixed and Other). Depending on the achieved power, this may be limited to a broader group of ethnicities (eg 'ethnicities other than White'). Once we know more about the quality of onboarding data and numbers of patients enrolled, we will make an assessment as to what is possible in terms of subgroup analyses.

Reporting

Our reporting of the study will aim to meet the requirements of the STROBE checklist for the reporting of cohort studies.³⁰

Power calculation

A set of power calculations for binary outcomes (eg ICU: yes/no) are shown in Table 1, below.

Table 1: Total sample sizes resulting from power calculations

| Total sample sizes (N) | | Relative risk in treated group | | |
|---------------------------|-------|--------------------------------|--------|---------|
| | | 50% | 75% | 90% |
| Baseline risk | 10.0% | 870 | 4,010 | 26,990 |
| | 5.0% | 1,812 | 8,404 | 56,816 |
| | 4.0% | 2,282 | 10,602 | 71,730 |
| | 3.0% | 3,068 | 14,266 | 96,584 |
| | 2.0% | 4,638 | 21,590 | 146,294 |
| | 1.0% | 9,346 | 43,568 | 295,422 |
| | 0.5% | 18,766 | 87,522 | 593,680 |

Note: equal sized treatment and control groups of N/2; full compliance assumed, two-sided tests; power 80%; alpha 5%.

The power calculations are based on standard large sample approximations. Power calculations using Fisher-based randomisation inference produce similar results to those based on large sample approximations. For example, assuming two equally sized groups, a two-sided test at the 5% significance level, and an outcome of 2% in the control group and 1.5% in the treated group, a sample size of around 22,000 (11,000 in each group) would be required to achieve a power of 80% (based on a simulation with 10,000 draws).

These power calculations demonstrate that relatively large samples will be required to identify treatment effects of CO@h on the primary outcomes, particularly for infrequent outcomes such as ICU admittance. For reference, the mixed-methods study of pilots of remote home monitoring models in England found that for the pre-hospital model of CO@h, approximately 8% of onboarded patients attended A&E, 5% were admitted to hospital in an emergency, 0.2% were admitted to ICU and 1% died.¹

Strengths and limitations

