As the PRINCIPLE trial also used an age threshold of age 65 for trial inclusion, there is a risk that this will introduce bias in our analysis. We will limit the risk of the PRINCIPLE trial biasing our results by checking the number of patients enrolled in the trial by area and age band and end the study period of our evaluation before a maximum of 5% of patients around the threshold have been enrolled in the PRINCIPLE trial.

This analysis builds on the assumption that there are no other differences in care of patients above and below 65 years of age that would affect the hospital outcomes of COVID-19 positive patients. We do not know of any such interventions but, if they exist, they may bias our results. We may be able to indirectly examine this to a certain extent by checking that there is no discontinuity in outcomes at age 65 in a period before the CCGs implemented CO@h (ie the 'placebo outcomes' sensitivity analysis).

There is a substantial risk to the execution and validity of the study if we cannot access onboarding data. Currently onboarding data is potentially going to be delayed, especially from CCGs that have been badly hit by the third pandemic wave, and/or may be incomplete. These data are necessary to allow us to estimate the effect of being enrolled in CO@h. In its absence, we can run an intention-to-treat analysis, estimating the effect of treatment eligibility, ie treat all non-CEV patients aged 65 or above as receiving CO@h and all non-CEV patients below as not receiving the intervention (a 'sharp' design). However, it is possible that compliance will not be high; therefore, this analysis is less likely to find an effect even if onboarding did affect outcomes, due to the added noise of non-compliers. It may however still provide a useful indication in the absence of onboarding data: a significant intervention effect would indicate that CO@h affected patients' outcomes (subject to sensitivity analyses), while a lack of a statistically significant effect would be non-informative as it would not be possible to unpick whether this is due to low uptake of the CO@h programme, the 65+ threshold not being complied with, or the CO@h programme not having the anticipated effect on outcomes.

If interim analyses are performed before receipt of final data, only the final analyses may be published.

Acknowledgements

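### The main fuzzy analysis is declared to estimate a complier effect, but the only point estimate described is the unscaled eligibility (intention-to-treat) difference across age 65

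*SAP*

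**What the plan says.** - **Estimand.** SAP, Sharp and fuzzy designs: if reliable onboarding data are available, the main analysis is fuzzy and its estimates concern compliers only.
- **Statistic.** Same section: "the fuzzy design is operationalised using the Anderson-Rubin statistic", a contrast of adjusted responses between those assigned to treatment and to control. The SAP then restates this as the difference between two outcome regressions on either side of the threshold, and calls the result the effect on the treated.
- **Point estimate.** SAP, Main analysis: "we will estimate a treatment effect based on the difference in means between the treated and untreated". The polynomial is of order zero, and the p-values are for zero effect.
- **Reporting scale.** Same section: for binary outcomes, "the estimated treatment effects will comprise differences in mean outcomes on the per cent scale"; for the others, differences in mean bed days. The interval comes from inverting the Fisher p-value.
- **Sharp analysis.** SAP, Sensitivity analyses, item 1: "we will use a sharp design (without taking account of compliance/oximeter receipt) to estimate the average effect of intervention eligibility at age 65".
- **Comment on the sharp analysis.** SAP, Strengths and limitations, on the case without onboarding data: "this analysis is less likely to find an effect even if onboarding did affect outcomes, due to the added noise of non-compliers".

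**The concern.** A complier effect needs two quantities: the outcome difference across 65 and the enrolment difference across 65. The SAP examines the enrolment difference as a diagnostic but never uses it in a point estimate. An analyst who follows Main analysis as written would publish an eligibility effect under a complier label, closer to zero than the effect it claims to be. This applies to every outcome, including critical care use and death.

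Two things follow. The reported interval may not be on the same scale as the point estimate. And agreement between the main p-value and that of sensitivity analysis 1 could be taken as corroboration when the two tests are the same.

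**Working it through.** **Inputs**
- Outcome rates: the worked example under Power calculation, "an outcome of 2% in the control group and 1.5% in the treated group", a difference of -0.50 points.
- Sizing conditions: the footnote on power under Window selection, "Using power = 80%, alpha = 5%, and two-sided test". The note to Table 1 adds equal groups and full compliance.
- Enrolment jump at 65, written c: not given. Study design says the volume of referrals is unclear. The values of c below are assumptions.

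**1. The plan's own figure.** With p1 = 0.02, p2 = 0.015 and mean 0.0175,

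n per group = [1.960·√(2 × 0.0175 × 0.9825) + 0.8416·√(0.02 × 0.98 + 0.015 × 0.985)]² / 0.005²

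= (0.36345 + 0.15604)² / 0.000025 = 10,795, or 21,590 in total.

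This is the Table 1 entry. It assumes c = 1, the one case in which the eligibility effect and the complier effect coincide, so the sizing does not expose the problem.

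**2. What the statistic is.** Let Z = 1 for age 65 or over, D = 1 if enrolled, and Y the outcome. The Anderson-Rubin contrast at a hypothesised effect τ0 is

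AR(τ0) = mean(Y - τ0·D | Z=1) - mean(Y - τ0·D | Z=0) = ΔY - τ0·ΔD,

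where ΔY and ΔD are the differences across 65 in mean outcome and in proportion enrolled.
- It is zero at τ0 = ΔY/ΔD. That ratio is the complier estimate belonging to this statistic, and the SAP does not state it.
- With an order-zero polynomial, the difference between the two outcome regressions is ΔY alone. So is the difference in means by side of 65.
- At the stated null, τ0 = 0 and Y - 0·D = Y. Receipt drops out and AR(0) = ΔY, the statistic of the sharp analysis in the same patients and window. The outcome-by-outcome recoding of receipt for patients enrolled after A&E therefore changes neither this p-value nor the described point estimate.

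**3. Size of the gap.** If eligibility acts only through enrolment, ΔY = c × complier effect. For a true effect of -0.50 points:

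| Assumed jump c | Difference in means reported (points) | Complier effect ÷ reported |
|---|---|---|
| 1.0 | -0.50 | 1 |
| 0.8 | 0.8 × -0.50 = -0.40 | 1.25 |
| 0.5 | 0.5 × -0.50 = -0.25 | 2 |
| 0.3 | 0.3 × -0.50 = -0.15 | 3.3 |

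Simulation agrees (2,000 datasets per setting, 10,795 per side, 10% assumed to be enrolled whatever their age). At c = 0.5 and 0.3 the difference in means averaged -0.24 and -0.15, while the ratio had medians of -0.49 and -0.53.

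**4. Identity of the p-values.** In one simulated dataset, with the same 10,000 draws, the Fisher p-value was 0.7205 for both the sharp test and the Anderson-Rubin test at zero. The largest gap between the two statistics over all simulated datasets was 0.

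**5. Scale of the interval.** In that dataset the jump was 0.302 and ΔY was 0.07 points. Inverting the large-sample form of the test over τ0·D gave -0.94 to 1.42 points; inverting over τ0·Z gave -0.28 to 0.43. The widths, 2.36 and 0.71, differ by a factor of 3.3, which is 1/0.302. The SAP's sentence on the interval fits either.

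**The case against.** The strongest defence is that the pieces are already in the plan: the estimand is compliers, the statistic is Anderson-Rubin by assignment, receipt is defined for the fuzzy part, and the interval comes from test inversion. Inverted over receipt, that interval is a complier interval. This stands, and a reader who infers that the plan offers no route at all to a complier effect goes too far. What remains is that no point estimate on that scale is named, the inversion is not said to run over receipt, and the SAP's own paraphrase and reporting sentences describe the unscaled difference.

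Other stronger readings that the text does not support:
- **The main contrast is by receipt, and so confounded by who was enrolled.** The phrase treated and untreated is loose, but Sharp and fuzzy designs speaks of units assigned, and Local randomisation approach and Window selection use treated and control for the sides of 65.
- **The SAP is wrong that a sharp estimate understates the treatment effect.** That statement in Strengths and limitations is correct.
- **The remark on detection is simply false.** It names no comparator. Against full compliance it is true. It fails only against the fuzzy test of zero effect, the comparison its context suggests.
- **Sensitivity analysis 1 is redundant.** It targets a different estimand, the effect of eligibility, and is worth reporting.
- **This defect costs power.** Non-compliance weakens the sharp and fuzzy tests alike, and the fix does not change that.

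**Conclusion.** The point holds. As written, the main analysis attaches a complier label to the eligibility difference. The reported value is the complier effect times the enrolment jump: about -0.25 or -0.15 points instead of -0.50 at assumed jumps of 50 or 30 points. The size rests on those assumed jumps and on eligibility affecting outcomes only through enrolment. Under that condition the shrinkage towards zero holds for any jump below 100 points.

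The equality of the two zero-effect p-values needs no such assumption. It is exact for the Anderson-Rubin test with a common set of draws; separate sets of draws would differ only by simulation error. Sensitivity analysis 1 thus adds an estimand but no independent evidence of significance. The mismatch of scale between estimate and interval is a possibility left open by the wording, not something the SAP prescribes.

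**What to change.** 1. In Main analysis, state the complier estimate as the difference in mean outcome by side of 65 divided by the difference in proportion enrolled by side of 65 (Wald/2SLS). Align the paraphrase of the statistic in Sharp and fuzzy designs with this.
2. State that its 95% interval is the set of τ0 not rejected by the permutation test on Y - τ0·D, permuting age eligibility.
3. In the sentence on the difference in means, replace treated and untreated with eligible and ineligible, and label that contrast as the intention-to-treat effect.
4. State that the p-value for zero effect is shared by the fuzzy and sharp analyses. In Strengths and limitations, clarify that the sharp analysis is less likely to find an effect than under full compliance, not than the fuzzy test of zero effect.

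Promoting the intention-to-treat result to a co-main result is optional. The cost is SAP wording, plus one division and one specified test inversion per outcome. The data are the same, and the enrolment difference is already due to be examined in the diagnostic checks.

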At the time of writing, it is unclear what volume of patients have been referred to the CO@h pathway, and what onboarding data will be available due to pressure on the system to cope with the pandemic. As a result, the study may be underpowered. This risk is further exacerbated by the fact that the primary outcomes relate to use of critical care beds and mortality. The mixed-methods study of pilots of remote home monitoring models in England

found that for the pre-hospital model of CO@h, although 10% (174/1,737) of patients that were monitored deteriorated and were escalated, 0.2% (3/1,737) of patients were admitted to ICU and 1% (20/1,737) died.¹ See the Power calculation section for further details

All decisions taken after this statistical analysis protocol (SAP) has been finalised will be documented and justified in an addendum to it. We may run interim analyses on incomplete data to provide the CO@h programme team with some preliminary indications of results. The results of the final analysis will be published in line with the Health Foundation's Improvement Analytic Unit's (IAU's) aim of openness and transparency.

Study outcomes

We will analyse outcomes in the 28-day period following a COVID-19 positive test (ie equal to or less than 28 days from a positive test, with the date of the first COVID-positive test being equal to day zero). We are limiting most of the outcomes to binary variables (ie capturing whether there was an A&E attendance rather than the number of attendances); this is because of the short follow-up period and likely sparsity in hospital event counts other than 0 and 1 (which we will confirm on receipt of the data). The following outcomes will be included:

- Type 1 A&E attendance (binary outcome yes/no)
- Emergency admission (binary outcome yes/no)
- Critical care bed use (binary outcome yes/no)
 - This will capture a stay in ICU at any point during an admission, which could be as a result of either an emergency or an elective admission.
 - This variable includes level 2 and level 3 beds, as well as beds under code 5 (flexible critical care beds where there is a mix of level 2 and level 3 beds) and code 90 (temporary use of non-critical care beds).¹²
- Total emergency hospital bed days

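### The SAP's only confidence interval, obtained by inverting the Fisher p-value, is unreliable for binary outcomes when a window holds few events: with none it can be exactly [0, 0]

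*SAP*

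**What the plan says.** Under Main analysis in the SAP, "we will estimate a treatment effect based on the difference in means between the treated and untreated". Outcomes are not transformed, and "we will use a polynomial of order zero". For the test, "10,000 simulated draws based on Fisher's exact approach to null-hypothesis testing will be used to estimate p-values of zero effect", and "The null hypothesis for the Fisher-based simulation will assume complete randomisation of patients to treatment within the window". The interval follows from the test: "A confidence interval will be estimated for the treatment effect by inverting the calculation for the Fisher-based p-value". Effect values that are not rejected form the interval. The Neyman approach adds a p-value and its power, but no interval is stated for it. If the two approaches disagree, the number of observations decides, "with the Fisher framework being preferred where sample sizes within the window are small".

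For the fuzzy design (Sharp and fuzzy designs), the Anderson-Rubin statistic is "the difference in the adjusted, transformed responses between units assigned to treatment and control".

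Critical care bed use and death are two of the three primary outcomes; the third is critical care bed days. The pilot figures quoted under Study design are "0.2% (3/1,737) of patients were admitted to ICU and 1% (20/1,737) died".

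Sensitivity analysis 4 repeats the analysis of each primary outcome in smaller windows, down to 10 patients per side, and plots estimates with intervals. The SAP sets no minimum number of events and no rule for a window with none.

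**The concern.** To test a non-zero effect by randomisation, each patient's unobserved outcome has to be filled in. The SAP names no model for this. For a difference in means the obvious one is a constant shift: subtract the same value from every treated patient or, in the fuzzy form, from every patient who received the intervention. For a 0/1 outcome this is impossible. A shift of -0.1 percentage points cannot be any one patient's effect.

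With many events this matters little, because the test behaves like a large-sample comparison of means. With few events, the shifted data show almost no variation within groups, so nearly every non-zero value is rejected and the interval shrinks as information disappears. A null result on critical care could then appear with a very short or zero-width interval and be read as ruling out both benefit and harm. The window plot, meant to show how stable the result is, could show intervals collapsing as data are removed.

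**Working it through.** **Inputs.** From the SAP: difference in means, order-zero polynomial, complete randomisation, two-sided 5%, pilot risks 3/1,737 = 0.17% (ICU) and 20/1,737 = 1.15% (death), and a 10-per-side minimum. Assumed: relative risk 0.5, equal groups, and enrolment of 30% above and 2% below age 65 (also 10% v 2% and 5% v 1%), because the SAP gives no uptake figures. Effects are treated minus control.

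**The SAP's own figure first.** Table 1, 2% v 1.5%: n per group = [1.96·√(2 × 0.0175 × 0.9825) + 0.8416·√(0.02 × 0.98 + 0.015 × 0.985)]² / 0.005² = 10,795, so N = 21,590, as printed. All 21 cells reproduce. Simulated Fisher power at 11,000 per group was 79.95%, in line with the SAP's statement. The test of zero effect is sound.

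**Zero events, sharp design.** For a candidate effect τ ≠ 0, the adjusted outcomes are -τ for every treated patient and 0 for every control. The observed difference, -τ, is the most extreme possible. Only the actual allocation and its mirror image reach it, so p = 2/C(2n, n). At n = 10 per side that is 2/184,756, about 0.00001. Every τ except 0 is rejected.

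**Zero events, fuzzy design.** The adjusted outcome is -τ × receipt, so for every τ ≠ 0 the p-value equals that of the enrolment comparison. If that is significant the set is {0}; if not, it is the whole line. With 30% v 2% uptake, the set is unbounded at 10 per side (p = 0.21) and {0} from 20. With 10% v 2% it is {0} by about 100 per side, and with 5% v 1% by about 250.

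**How often this arises.** With risk 0.2% in both groups, the chance of no event is 0.998^(2n): 96%, 82% and 37% at 10, 50 and 250 per side. For death at 1% it is 82%, 37% and 0.7%.

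**Few events, sharp design, percentage points:**

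| Per side | Events, control v treated | Inverted Fisher | Newcombe |
|---|---|---|---|
| 500 | 0 v 0 | 0 to 0 | -0.76 to +0.76 |
| 500 | 1 v 0 | -0.42 to 0.00 | -1.12 to +0.58 |
| 1,000 | 1 v 1 | -0.20 to +0.20 | -0.47 to +0.47 |
| 1,000 | 3 v 1 | -0.60 to +0.20 | -0.78 to +0.30 |
| 10 | 3 v 1 | -60 to +22 | -51 to +16 |

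For 0 v 0, the Newcombe limit is 1.96²/(n + 1.96²): 3.84/503.84 = 0.76%. The last row shows that the inverted interval is not always the shorter one.

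**Coverage, sharp design, 0.17% risk, relative risk 0.5:**

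| Per side | Population risk difference | Average effect among patients in the window |
|---|---|---|
| 200 | 29% | 89% |
| 500 | 58% | 85% |
| 1,000 | 82% | 89% |
| 2,000 | 93% | 94% |

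The first three population figures have a simple source. The interval can contain the true -0.086 points only if the control group has at least one event. That chance is 1 - (1 - 0.001727)^n: 29%, 58% and 82%. The right-hand column assumes that no patient is harmed; it is simulated, and its last two entries move by one or two points between runs.

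At 1.15% risk, population coverage is 89%, 94%, 95% and 95%. In the fuzzy design (30% v 2%, 0.2% risk) it is 40% and 85% at 250 and 1,000 per side.

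**Where it fades.** At 1% risk and relative risk 0.5, 1,000 per side gives 1,000 × (0.01 + 0.005) = 15 expected events and 94.5% coverage. A Table 1 window for the same case (9,346 in total, 4,673 per side) expects 4,673 × 0.015 = 70 events; coverage there is 95%.

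**The case against.** The strongest reply concerns the target. Fisher inference treats only assignment as random, and the SAP describes an effect for patients inside the window. On that target the shortfall is modest, as the right-hand column shows, and the 29% figure largely reflects extending the result to a wider population. This stands. The SAP does not say which target it means, so both belong on the page. Neither makes a zero-width interval acceptable.

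Second, the main window may be large. The cohort could be national and the SAP anticipates about five years either side, so it may hold enough events. This also stands. The documents do not fix the window's size, however, and the SAP warns that primary-outcome numbers could be very small.

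Third, 0.17% is ICU admission among monitored pilot patients. The SAP's outcome also counts level 2, flexible and temporary beds, and its cohort is everyone with a first positive test. The rate is therefore an assumption.

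Fourth, the preference for Fisher in small windows does not cause the fault: a plug-in Neyman standard error is also zero at 0 v 0.

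Fifth, the SAP reports group estimates and Neyman power and acknowledges low power. A reader would see 0 v 0, but low power should produce a wide interval, and this method produces the opposite.

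**Conclusion.** The point holds within limits. Under the constant-shift reading, which the SAP does not spell out but for which it offers no alternative, the planned interval is degenerate with no events and usually much too short with one to three events in windows of several hundred or more per side. It affects the small-window plot, any subgroup analysis, and a main window with few critical care events or deaths. Critical care bed days collapse in the same way when nobody has any (same algebra, not simulated).

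A reader might infer that every primary-outcome interval will be falsely precise, or that the main analysis has 29% coverage. The documents do not support that. Coverage is near 95% once about 10 events are expected, a window of Table 1 size is largely unaffected, the fuzzy set may be unbounded rather than zero-width, and in tiny samples the interval can be the wider one. Nor does the fault touch the p-value for zero effect. The sizes rest on the assumed pilot risk, relative risk 0.5 and assumed uptake. The change should be made before the intervals are produced.

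**What to change.** Keep the Fisher p-value for the test of zero effect. Then:

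- For binary outcomes, report the eligibility (sharp) risk difference with a score-type interval, Newcombe or Miettinen-Nurminen, in every window.
- Show the inverted Anderson-Rubin interval on the complier scale only if a pre-set minimum number of events across both groups is reached (for example 10) and the enrolment jump in that window is significant. Otherwise give the eligibility interval and the event counts. Dividing the eligibility limits by the enrolment jump is not an adequate substitute, because it ignores uncertainty in the jump.
- For bed days, require the same minimum number of patients with a non-zero value before showing an inverted interval. Otherwise state that there are too few events to estimate, and print the counts.
- Apply these rules to the main analysis, the window plot in sensitivity analysis 4 and the subgroups.

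The threshold of 10 is a convention, suggested by where coverage recovers; it should be fixed before outcome data are seen. At relative risk 0.5, Newcombe coverage was 94.8% to 100% for risks of 0.2% and 1%; at relative risk 1 the lowest cell was 93.5%. The cost is SAP wording and a few lines of code. The downside is wider, slightly conservative intervals and fewer complier-scale intervals when events are few.
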